Study Protocol and Statistical Analysis Plan

Study title: The Effects of Wild Blueberries on Depressive Symptoms in Young Adults

Acronym: BluMood

Date: 07 April 2022

1. Sample Size Calculation

A mixed-design ANOVA carried out on data from a previous study in adolescents demonstrated a medium effect size (partial $\eta^2 = 0.04$) of a four-week blueberry intervention on depressive symptoms (Fisk, Khalid, Reynolds, & Williams, 2020). An *a priori* power analysis in G*Power with this effect size indicated that a sample of 60 participants would be necessary to achieve a power level of 0.80 at a significance level of 0.05.

2. Recruitment and Screening

Participants will be recruited using opportunity sampling. The study will be advertised through email distribution and with posters across the University of Reading. Before interested participants are enrolled in the trial, we will invite them to the lab for a screening session to determine if they meet the eligibility criteria and give them an opportunity to become familiar with the cognitive task battery so as to reduce the influence of practice effects. Participants will be compensated with £120 (\$156) for completing all phases of the study.

3. Randomization and Blinding Process

A researcher not involved in recruitment or data collection will use blocked randomization with random permuted blocks of two and four individuals to form the allocation list for the two comparison groups. The allocation sequence will be generated using the online randomization tool Sealed Envelope (v1.19.1) and will be concealed to the researchers enrolling and assessing participants. The interventions for chronic consumption will be distributed to participants in opaque, sealed sachets whereas on testing days the intervention drinks will be administered in opaque shaker bottles prepared by research personnel not involved in the conduct of the trial. Thus, both participants and investigators will be blinded to the treatment assignment throughout the study.

4. Testing Protocol

Visit 1

09:00 – participants consume a standard breakfast of oat porridge after an overnight fast

09:40 – participants complete cognitive task + PANAS-X

10:00 – blood sample taken

10:10 – participants consume the drink they have been allocated to (blueberry or placebo)

11:10 – participants complete a battery of questionnaires (e.g. BDI-II, PHQ-9)

11:25 – participants have their heart rate variability measured

12:10 – participants complete cognitive task + PANAS-X

12:25 – participants are given a bag with 41 sachets for the chronic phase of the study

Visit 2

09:00 – participants consume a standard breakfast of oat porridge after an overnight fast

09:30 – participants complete a battery of questionnaires (e.g. BDI-II, PHQ-9)

09:50 – participants have their heart rate variability measured

10:00 – participants complete cognitive tasks + PANAS-X

10:25 – blood sample taken

5. Statistical Analysis Plan

The outcomes will be analyzed using ANCOVAs adjusted for baseline values, sex, and habitual fruit and vegetable consumption as long as the assumptions for conducting the analysis are met.

References

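### The claim that 60 participants give 0.80 power for partial eta-squared 0.04 cannot be reproduced from its stated inputs and is not calculated for the planned ANCOVA

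*Combined protocol and SAP*

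**What the plan says.** Section 1 (Sample Size Calculation) is the only justification of the sample size. It cites an earlier study: "A mixed-design ANOVA carried out on data from a previous study in adolescents demonstrated a medium effect size", given as partial eta-squared 0.04. It then says that a G*Power analysis with that effect "indicated that a sample of 60 participants would be necessary to achieve a power level of 0.80 at a significance level of 0.05". It names no G*Power test family, effect-size option, number of measurements, correlation between measurements or dropout allowance.

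Section 5 (Statistical Analysis Plan) specifies a different model: "The outcomes will be analyzed using ANCOVAs adjusted for baseline values, sex, and habitual fruit and vegetable consumption". No power is given for it.

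Section 3 describes "blocked randomization with random permuted blocks of two and four individuals to form the allocation list for the two comparison groups", which I take as 1:1 allocation. Section 4 has the depression questionnaires completed once at each visit: at Visit 1, "11:10 – participants complete a battery of questionnaires (e.g. BDI-II, PHQ-9)", and at Visit 2, "09:30 – participants complete a battery of questionnaires (e.g. BDI-II, PHQ-9)".

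**The concern.** Partial eta-squared belongs to a particular model. A value from a mixed-design ANOVA cannot be carried into a calculation for another test unless its definition is known. This matters especially in G*Power, whose repeated-measures options treat the same input in different ways. The default within-between option multiplies f² by a factor that depends on the number of measurements and their correlation. If 0.04 was computed from data, it already contains the gain from repeated measurement, and that option would count the gain a second time.

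Section 1 carries the whole argument that the trial is large enough. If the 0.80 does not apply to the Section 5 test, the chance of missing an effect of the earlier size could be well above the implied 20%, and a null result could be read as stronger evidence than it is. As written, the plan does not let a reader tell whether that is so.

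**Working it through.** **Inputs from the plan.** Partial eta-squared 0.04, alpha 0.05 and power 0.80 (Section 1); two groups, taken as 1:1 (Section 3); three covariates (Section 5). Sidedness is not stated; the F test is taken as equivalent to a two-sided test.

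**Assumptions not in the plan.** The correlation r between measurements; two time points in the earlier ANOVA (chosen to match the two questionnaire sessions in Section 4); the share R of residual variance explained by sex and diet.

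**Step 1. Convert the effect.** f² = 0.04/(1 − 0.04) = 0.04167, so f = 0.204 and, for two equal groups, d = 2f = 0.408.

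**Step 2. Try to reproduce 60.** In G*Power's default within-between option with m measurements, the noncentrality is λ = f²·N·m/(1 − r), with df (m − 1) and (N − 2)(m − 1). For m = 2, taking even N:

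| r | N for 0.80 | λ at N = 60 | Power at N = 60 |
|---|---|---|---|
| 0 | 98 | 5.00 | 0.594 |
| 0.3 | 68 | 7.14 | 0.748 |
| 0.4 | 60 | 8.33 | 0.810 |
| 0.5 | 50 | 10.00 | 0.875 |

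With m = 3, 60 arises at r of about 0.24 to 0.27. Other G*Power choices give 144 (between-factors test, m = 2, r = 0.5), 192 (Cohen option) and 194 (SPSS option). So 60 can be reached, but only with a setting that Section 1 does not report.

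**Step 3. What 60 gives for the planned ANCOVA.** λ = f²·N, df 1 and N − 5 = 55. Power of 0.80 requires f² = 0.1355, so partial eta-squared = 0.1355/1.1355 = 0.119, f = 0.368 and d = 0.74 in covariate-adjusted SDs. This does not depend on how the earlier 0.04 was defined. If 10% were lost (an assumption), 54 analysed would give 0.131 (d = 0.78).

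**Step 4. ANCOVA power for 0.04 under three readings.**

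*(a) 0.04 is the ANCOVA effect.* λ = 0.04167 × 60 = 2.5; power 0.34; 191 needed for 0.80.

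*(b) 0.04 is a group-by-time value computed from two time points.* That effect is measured against the variance of the change, 2(1 − r)σ². The ANCOVA residual variance is (1 − r²)σ². The ratio is 2/(1 + r), so f² for the ANCOVA = 2 × 0.04167/(1 + r). If sex and diet explain a share R of residual variance, divide by (1 − R).

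| r | f² | Power at 60, R = 0 | N for 0.80 | Power at 60, R = 0.2 |
|---|---|---|---|---|
| 0 | 0.0833 | 0.594 | 97 | 0.690 |
| 0.5 | 0.0556 | 0.434 | 144 | 0.518 |
| 0.9 | 0.0439 | 0.357 | 181 | 0.429 |

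To reach 0.80 at 60, R would have to be at least 1 − 0.0833/0.1355 = 0.39 even at r = 0.

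*(c) 0.04 is on a scale that excludes the correlation.* The difference in change is 4f = 0.816 SD, so f² for the ANCOVA = (0.816/2)²/(1 − r²) = 0.1667/(1 − r²). Power at 60 is 0.87 at r = 0 and 0.95 at r = 0.5.

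**Step 5. Compare like with like.** Converting the detectable f² of 0.1355 back to the two-time-point ANOVA scale by (1 + r)/2 gives partial eta-squared 0.063 (r = 0), 0.092 (r = 0.5) and 0.114 (r = 0.9), that is 1.6 to 2.9 times 0.04.

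**The case against.** The strongest defence is that no arithmetic error is shown. The figure 60 is what G*Power's default within-between option returns with two measurements at a correlation of about 0.4, and at 0.5 only 50 would be needed. That stands: a reader might infer that 60 is a miscalculation, but the documents support only that it cannot be reproduced from what is stated.

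A reader might also infer that the trial is shown to be underpowered. It is not. The answer turns on how the earlier study's 0.04 was defined, and under reading (c) 60 is adequate. The number of earlier time points is unknown too. With three, equal correlations and a steadily growing effect (f² for the ANCOVA = 4f²/(1 + r)), power reaches 0.80 at correlations below about 0.23, or below about 0.54 if R = 0.2.

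Two further inferences go too far. Saying that the detectable 0.12 is three times the planning effect is right only if 0.04 is already an ANCOVA value; otherwise it compares two scales (Step 5). A miss rate of 41% to 66%, from 1 − 0.594 and 1 − 0.342, assumes that sex and diet explain nothing, although Section 5 adjusts for both. The two-session model is itself approximate, since the Visit 1 questionnaires at 11:10 follow the drink at 10:10.

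None of this supplies the missing settings or provides a calculation for the ANCOVA. Section 1 also describes 0.04 as the result of an ANOVA run on earlier data, which points towards a value that already includes the correlation.

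**Conclusion.** The point holds as a failure of reproducibility and a mismatch between the powered test and the planned test. What is firm, given 1:1 allocation and 60 analysed, is that the Section 5 ANCOVA has 80% power for partial eta-squared of about 0.12 (d about 0.74), and that Section 1 does not show 0.80 power for 0.04.

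The power for 0.04 itself is conditional: about 0.34 under reading (a); 0.36 to 0.59 under (b), or 0.43 to 0.69 if sex and diet also explain 20% of residual variance; 0.87 or more under (c). Reading (b) is the natural one for a value computed from data, so a shortfall is likely. The documents do not settle the matter, so it is not proven. The ranges rest on assumed correlations, two earlier time points and an assumed covariate contribution, and are illustrative.

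**What to change.** Keep 60 and make three changes to Section 1.

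1. Restate the power for the planned test: *With 60 analysed participants the ANCOVA in Section 5 has 80% power for partial eta-squared of about 0.12 (d about 0.74).*
2. State the G*Power test family, effect-size option, number of measurements, correlation and any dropout allowance, and say how the earlier 0.04 was defined: which effect, over how many time points, and whether it was computed from data.
3. Withdraw the claim of 0.80 power for 0.04 unless that definition supports it, as it would on a scale that excludes the correlation.

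The illustrative 34% to 59% range should not go into the protocol, because it rests on assumptions that the plan does not contain.

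Cost: wording only, with no extra participants and no change to design or analysis. The downside is that the stated power may become less favourable.

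### Does the missing drink in the Visit 2 timetable contradict the statement that drinks are given on testing days?

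*Combined protocol and SAP*

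**What the plan says.** Section 3 sets two forms of packaging against each other. The first half of the sentence covers home use: "The interventions for chronic consumption will be distributed to participants in opaque, sealed sachets". The second half covers drinks taken in the lab: "whereas on testing days the intervention drinks will be administered in opaque shaker bottles". It adds that the bottles are prepared by staff who take no part in running the trial, and concludes that participants and investigators are both blinded. It names no visit, time or number of drinks, and does not say who hands the drink over.

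Section 4 gives the clock schedule. At Visit 1: "10:10 – participants consume the drink they have been allocated to (blueberry or placebo)". That visit ends when "participants are given a bag with 41 sachets for the chronic phase of the study". At Visit 2 the steps are breakfast at 09:00 after an overnight fast, then "09:30 – participants complete a battery of questionnaires (e.g. BDI-II, PHQ-9)", heart rate variability at 09:50, cognitive tasks and PANAS-X at 10:00, and blood at 10:25. No drink or sachet is listed.

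Section 5 is a single sentence. It specifies ANCOVAs adjusted for baseline, sex, and habitual fruit and vegetable intake. It names no visit, primary outcome or contrast.

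**The concern.** Section 4 is headed as the testing protocol and has two visits, so both look like testing days. If drinks are given on testing days, a drink would be expected at each. Only one visit has a row for it.

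If the mismatch were real, the meaning of the follow-up comparison would be at stake. With no drink before the Visit 2 assessments, the ANCOVA measures the effect of repeated servings. With a drink before them, it measures that effect plus any acute response. The trial clearly has an interest in the acute response, because cognition and PANAS-X are taken before the Visit 1 drink and again two hours after it. If some participants had a drink before assessment at Visit 2 and others did not, the result would be a blend of the two. Section 5 does not say which contrast is meant, so the timetable is the only guide.

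**Working it through.** The plan states no figure for this point. The check sets the passages side by side and adds some simple arithmetic.

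**1. What each passage can settle.**

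| | Section 3 | Section 4, Visit 1 | Section 4, Visit 2 |
|---|---|---|---|
| Purpose | concealment of product | timed schedule | timed schedule |
| Visit named | no | yes | yes |
| Clock time of drink | none | 10:10 | none listed |
| Drink placed relative to assessments | no | yes | no drink listed |

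The plural in Section 3 can refer to the Visit 1 days of many participants. Nothing in that section puts a drink ahead of the Visit 2 assessments, so no two statements on that question conflict.

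**2. Serving count (Section 4).** Visit 1 drink + sachets = 1 + 41 = 42, and 42/7 = 6.0 weeks. With a second drink, 42 + 1 = 43, and 43/7 = 6.14 weeks. One serving a day is an assumption, since the document gives neither the daily number nor the length of the chronic phase. The count favours the timetable as written but does not prove it.

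**3. Spacing (Section 4).** At Visit 1 the questionnaires start 60 minutes after the drink (10:10 to 11:10), and the repeat cognition and PANAS-X 120 minutes after it (10:10 to 12:10). The same spacing at Visit 2 would need a drink at 09:30 − 60 min = 08:30 for the questionnaires, or at 10:00 − 120 min = 08:00 for cognition. Both times precede the 09:00 breakfast that ends the overnight fast. The Visit 2 schedule therefore has no room for a drink with the Visit 1 spacing, which again fits the reading that none is planned before the assessments.

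**4. Effect on the comparison.** The drink is blueberry or placebo according to allocation. A drink given to everyone at Visit 2 would be given in both arms, so randomisation still protects the comparison, and only its interpretation would shift. A drink after the 10:25 blood sample would follow every listed assessment and shift nothing.

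**5. Can the shift be sized?** Only with numbers from outside the document. Section 1 gives partial eta-squared 0.04, so f = sqrt(0.04/0.96) = 0.204. Read as a simple two-group effect, d = 2f = 0.408. Assumed acute effects of 0.1 and 0.3 SD would be 0.1/0.408 = 24.5% and 0.3/0.408 = 73.5% of that. These percentages cannot be relied on. The document gives no acute effect. The 0.04 comes from a mixed-design ANOVA whose term is not named, and d = 2f in units of the outcome SD does not generally hold for a group-by-time term. The calculation also assumes that the full acute effect is present at Visit 2, with the timing unknown. The shift is zero if there is no acute effect or no drink before the assessments.

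**The case for a change.** The strongest case for acting is that nothing in the document closes the question outright. The length of the chronic phase, the study day of Visit 2, the daily number of sachets and the timing of the last one are all unstated, so the 42-serving argument leans on an assumption. Section 5 is too short to help. The people who prepare bottles are not the people who run visits, so each group might work from a different section. A clarifying sentence would cost almost nothing.

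Part of this stands. The plural is loose, and the serving count is supporting evidence only. The fear of mixed practice is weaker. Section 3 separates those who prepare the bottles from the conduct of the trial, but does not have them administer the drinks. Those who run Visit 2 work to a timetable with no drink slot. Nothing in the text suggests that participants would be handled differently from one another. The silence of Section 5 about which contrast it estimates is a real gap, but a different one: an unstated contrast is not two conflicting ones. That an edit is cheap does not show that the plan is wrong without it.

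**Conclusion.** The concern does not hold as a contradiction in design or analysis. What remains is a clerical mismatch: a general phrase in a blinding paragraph against a specific timetable. Following the timetable as written gives a coherent Visit 2 comparison, with no drink listed before any assessment and both arms handled alike. The sample size of 60, the ANCOVA model and its covariates are untouched.

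This rests on two premises: that visits are run to the Section 4 timetable, and that the plural in Section 3 is not meant to add a Visit 2 drink before the assessments. The once-daily assumption behind the six-week count supports the second premise but is not essential to it. If the sponsor edits the document for other reasons, the two passages can be reconciled then by stating whether any drink or sachet is taken on the Visit 2 day and when. What is given that day is the sponsor's decision. No change to the plan follows from this point.

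### BDI-II, PHQ-9 and heart rate variability have no listed reading before the first randomised drink, yet Section 5 adjusts for a baseline it does not define

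*Combined protocol and SAP*

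**What the plan says.** Section 4 gives clock times for Visit 1. Two sets of measurements precede the randomised drink: "09:40 – participants complete cognitive task + PANAS-X" and "10:00 – blood sample taken". The drink comes next: "10:10 – participants consume the drink they have been allocated to (blueberry or placebo". The depression questionnaires and HRV come only after it: "11:10 – participants complete a battery of questionnaires (e.g. BDI-II, PHQ-9" and "11:25 – participants have their heart rate variability measured". Both are listed again at Visit 2, at 09:30 and 09:50.

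Section 5 is a single sentence. It proposes ANCOVA for the outcomes, with baseline, sex and usual fruit and vegetable intake as covariates, provided the method's assumptions hold. It does not say which assessment is the baseline for any outcome.

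Section 2 describes a session before enrolment: "we will invite them to the lab for a screening session to determine if they meet the eligibility criteria". It also lets participants practise the cognitive tasks. It names no questionnaire and no HRV recording.

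**The concern.** Depressive symptoms are the title outcome and the basis of the sample size in Section 1. If the timetable is followed as written, the only listed reading that could serve as their baseline is taken an hour after the first randomised drink. The same holds for HRV.

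Randomisation balances, on average, only what is fixed before treatment. If the drink moves the covariate, the adjusted difference no longer estimates the full effect of treatment. An acute shift in the same direction as the Visit 2 effect hides part of the benefit, and an opposite shift inflates it. Without a pre-drink reading, an acute effect cannot be told apart from chance imbalance between the arms, so the trial could not show which case applies.

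The plan itself treats acute change as worth measuring, because it repeats two assessments after the drink: "12:10 – participants complete cognitive task + PANAS-X". HRV has a further difficulty. If the 11:25 recording is meant as an acute outcome and not as a baseline, it has no listed baseline at all, and the Section 5 model cannot be fitted to it as written.

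**Working it through.** **Timing (Section 4).** Minutes are counted from the 10:10 drink.

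| Measure | Visit 1, before drink | Visit 1, after drink | Visit 2 |
|---|---|---|---|
| Cognitive task, PANAS-X | 09:40 (−30) | 12:10 (+120) | 10:00 |
| Blood | 10:00 (−10) | none | 10:25 |
| BDI-II, PHQ-9 | none listed | 11:10 (+60) | 09:30 |
| HRV | none listed | 11:25 (+75) | 09:50 |

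This part is certain from the document. The rest is illustration, because the document gives no acute effect, no correlation between readings and no effect in SD units.

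**Effect of the covariate.** Let delta be the effect at Visit 2, a the effect on the post-drink Visit 1 reading, and b the ANCOVA slope. The adjusted difference estimates delta − b × a, so the bias relative to the total effect is −b × a. With equal SDs at the two visits, b equals the correlation rho.

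**Size of delta.** Section 1 gives partial η² = 0.04 and says only: "A mixed-design ANOVA carried out on data from a previous study in adolescents demonstrated a medium effect size". I assume that this is the group-by-time effect on a two-point change score.
- f = sqrt(0.04/0.96) = 0.204, so d on the change scale = 2 × 0.204 = 0.408.
- In raw SD units, delta = 0.408 × sqrt(2(1 − rho)). This is 0.408 at rho = 0.5 and 0.316 at rho = 0.7.

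The planned N of 60 can be reproduced only by adding inputs that Section 1 does not give. One example is a two-group, two-measurement interaction with a correlation of 0.39 to 0.40. Nothing below depends on that.

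**Bias.**
- rho = 0.5, a = 0.1 SD: 0.05 SD, and 0.05/0.408 = 12%.
- rho = 0.5, a = 0.2 SD: 0.10 SD, and 0.10/0.408 = 24%.
- rho = 0.7, a = 0.2 SD: 0.14 SD, which is 34% of 0.408 or 44% of 0.316.

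**Error rates.** I take 30 per arm (60 split equally) and a two-sided 0.05 test, using the noncentral t with 57 df. At rho = 0.5 the SE is sqrt((2/30) × (1 − 0.25)) = 0.224 SD.

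| a (SD) | Type I error (delta = 0) | Power at 0.408, a in same direction | Power at 0.408, a in opposite direction |
|---|---|---|---|
| 0 | 0.050 | 0.435 | 0.435 |
| 0.1 | 0.056 | 0.350 | not computed |
| 0.2 | 0.072 | 0.273 | 0.608 |

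Simulation with 40,000 runs agrees to within about 0.015. The 43% at a = 0 comes from the effect-size conversion and has nothing to do with the timetable. Only the movement away from it is relevant here.

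**A version without that conversion.** Suppose the analysis has 80% power when a = 0, and the acute effect is a fraction q of delta in the same direction. The share retained is 1 − b × q. At b = 0.5:
- q = 25% retains 0.875, and power falls to about 69%.
- q = 50% retains 0.75, and power falls to about 56%.

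**The case against.** The strongest reply is that not listed does not mean not measured. Section 4 is brief. It gives no time for collecting fruit and vegetable intake, although Section 5 needs it. The questionnaire battery is named by example only, and the eligibility measures are not itemised. A depression score could have been taken at screening. This stands as a limit: what is certain is that baseline is undefined and that no pre-drink reading is listed. That the 11:10 score will serve as the covariate is an inference, though a natural one, because Visits 1 and 2 form the only listed pair.

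Second, an acute effect on BDI-II or PHQ-9 after one hour may be small. It is more plausible for HRV. That is fair, and it means the risk may be lower for the title outcome than for HRV. As scheduled, however, the trial could not demonstrate it.

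Third, bias is relative to an estimand, and the plan states none. If the intended target were the effect of the chronic phase beyond the first drink, a post-drink covariate could be deliberate. The plan would then have to say so, and it does not.

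Fourth, questionnaires placed ahead of the pre-drink PANAS-X and cognitive task might influence them. This is a reason to choose the order with care, not a reason to leave the readings after the drink.

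**Conclusion.** The concern holds. BDI-II, PHQ-9 and HRV have no listed reading before the randomised drink. Their Visit 1 readings fall 60, 60 and 75 minutes after it, and Section 5 does not define baseline. If the schedule is followed and no screening score is used, the adjustment for the title outcome relies on a post-treatment covariate.

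The resulting bias is −(slope × a). Its size is unknown and it is zero if there is no acute effect. Under the assumed inputs, acute shifts of 0.1 to 0.2 SD at a correlation of 0.5 move the estimate by 12% to 24% of a 0.41 SD effect. At other correlations the percentages depend on how partial η² is converted. This should be fixed because the gap touches the main outcome, the remedy is cheap, and a pre-drink reading missed at Visit 1 cannot be taken later.

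**What to change.** **Schedule.** At Visit 1, take BDI-II, PHQ-9 and HRV before the drink. The order is open. Placing the questionnaires after the existing PANAS-X and cognitive task would leave those baselines undisturbed.

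**Section 5.** Define baseline as the last pre-drink value of each outcome. State whether the 11:25 HRV is an acute outcome. If it is, keep a post-drink recording and adjust it for the new pre-drink one.

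**Participants already tested.** Use a pre-drink screening score as baseline if one exists. Otherwise report the analysis both with and without the post-drink covariate, and say plainly that the covariate is post-treatment. Which of the two is primary is a judgement, to be fixed and justified before unblinding.

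**Cost in time.** Assume assessments start at 09:30, as at Visit 2.
- Visit 1 slot lengths, with HRV as at Visit 2: 15 (questionnaires) + 10 (HRV) + 20 (cognitive task, PANAS-X) + 10 (blood) = 55 minutes. The drink moves to 10:25 and the two-hour test to 12:25, a delay of 15 minutes.
- Visit 2 slot lengths: 20 + 10 + 25, plus 10 for blood, = 65 minutes. The times become 10:35 and 12:35, a delay of 25 minutes.
- The 10 minutes for HRV is the Visit 2 slot. If the recording takes longer, the delay grows by the same amount.

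No new instrument or staff is needed. There is one extra HRV recording if the acute one is kept.

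**Cost in precision, only for participants without a pre-drink score.** Dropping the covariate multiplies the SE by 1/sqrt(1 − rho²).
- At rho = 0.5 the factor is 1.155, and power falls from about 43% to 34% at 0.408 SD.
- At rho = 0.7 the factor is 1.40, and power falls from about 39% to 23% at 0.316 SD.

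For a same-direction shift, dropping the covariate gains power only if a exceeds delta × (1 − sqrt(1 − rho²))/rho. That is about 0.11 SD at rho = 0.5. At rho = 0.7 it is 0.13 SD for delta = 0.316 or 0.17 SD for delta = 0.408. This is why both analyses should be shown.

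### The only listed Visit 1 depression score is taken 60 minutes after the allocated drink, so the planned baseline adjustment conditions on a post-treatment value, and no sensitivity analysis uses the pre-drink mood score

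*Combined protocol and SAP*

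**What the plan says.** Section 5 (Statistical Analysis Plan) is one sentence: the outcomes are analysed by ANCOVA "adjusted for baseline values, sex, and habitual fruit and vegetable consumption", provided the assumptions are met. It does not define baseline values; the natural reading is each outcome's own Visit 1 score. PANAS-X is not named as a covariate for the depression outcomes.

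Section 4 (Testing Protocol) gives the Visit 1 order:

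- "09:40 – participants complete cognitive task + PANAS-X"
- the allocated drink, blueberry or placebo, at 10:10
- "11:10 – participants complete a battery of questionnaires (e.g. BDI-II, PHQ-9")
- the cognitive task and PANAS-X again at 12:10

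At Visit 2 the depression questionnaires come at 09:30.

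Section 2 (Recruitment and Screening) describes an earlier contact: "we will invite them to the lab for a screening session". Its stated purposes are eligibility and practice on the cognitive tasks. No mood or depression score is listed there.

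**The concern.** A baseline covariate is safe in a randomised comparison because allocation cannot have affected it. The 11:10 score lacks that guarantee. The trial itself repeats PANAS-X two hours after the drink, which suggests that it regards a same-day effect on mood as possible. If the drink moves the 11:10 score, the ANCOVA subtracts part of the treatment effect along with the baseline difference. An early benefit in the same direction as the six-week benefit would pull the estimate towards zero.

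The trial does hold a mood score that treatment cannot have touched, the 09:40 PANAS-X, but no planned depression analysis uses it. As written, a reader of the results could not tell whether the depression estimate depends on the post-drink score.

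**Working it through.** **Timing.** PANAS-X at 09:40 is 30 minutes before the drink (10:10 − 09:40). BDI-II and PHQ-9 at 11:10 are 60 minutes after it (11:10 − 10:10). In the listed schedule, 09:40 PANAS-X is the only pre-drink mood score.

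**Inputs.** N = 60 is from Section 1. The documents give no correlations, so these are assumptions, in standardised units with equal variances:

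- ρ, Visit 1 with Visit 2 depression score: 0.5 to 0.7, mid 0.6
- p, 09:40 PANAS-X with Visit 2 depression score: 0.35 to 0.50, mid 0.45
- c, 09:40 PANAS-X with Visit 1 depression score: 0.4 to 0.6, mid 0.5

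Allocation is taken as 1:1 with no dropout. Sex and fruit and vegetable intake are left out of the arithmetic.

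**Bias from the 11:10 score.** If the drink shifts that score by a, the adjusted estimate moves by about −ρ × a: half to 0.7 of the shift, 0.6a in the mid-case. The documents give no value for a.

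**Replacing the 11:10 score with PANAS-X.** Ratio of residual variances = (1 − p²)/(1 − ρ²).

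| Case | ρ | p | Ratio | Change | Equivalent N (60/ratio) |
|---|---|---|---|---|---|
| Best | 0.5 | 0.50 | 0.75/0.75 = 1.00 | 0% | 60 |
| Mid | 0.6 | 0.45 | 0.7975/0.64 = 1.25 | +25% | 48 |
| Worst | 0.7 | 0.35 | 0.8775/0.51 = 1.72 | +72% | 35 |

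If the own-baseline model had 80% power, the mid-case swap would have about 71% (noncentral F, noncentrality divided by 1.25). Degrees of freedom do not change.

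**Adding PANAS-X beside the 11:10 score.** R² = (ρ² + p² − 2ρpc)/(1 − c²); reduction = 1 − (1 − R²)/(1 − ρ²).

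- Mid-case: R² = (0.36 + 0.2025 − 0.27)/0.75 = 0.39; reduction = 1 − 0.61/0.64 = 4.7%.
- Largest (0.5, 0.50, 0.4): R² = 0.30/0.84 = 0.357; reduction = 1 − 0.643/0.75 = 14.3%.
- Smallest (0.7, 0.35, 0.5): p = ρc, so the reduction is 0%.

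The weight left on the 11:10 score is (ρ − pc)/(1 − c²). In the mid-case this is (0.6 − 0.225)/0.75 = 0.50, against 0.60 without PANAS-X. Most of the post-drink conditioning remains.

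**What a gap between the two estimates can show.** With no shift at 11:10, the two models still differ by chance. The variance of the difference is (ρ² + p² − 2ρpc) × 4/N. In the mid-case this is 0.2925 × 4/60 = 0.0195, so the SE is 0.14 SD and the 95% range is about ±0.27 SD. A shift would have to be about 0.27/0.6 = 0.46 SD before the gap it causes equalled that range.

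**The sample size of 60.** Section 1 cites partial η² = 0.04 from a mixed-design ANOVA, so f² = 0.04/0.96 = 0.0417. For a two-group by two-time interaction, with noncentrality f² × N × 2/(1 − repeated-measures correlation), N = 60 is reproduced at a correlation of 0.4 (power 0.81). As a plain between-group effect, the same f² gives 34% power at N = 60 and needs N = 192. The documents state neither the correlation nor the test chosen.

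**The case against.** **It is a preference, not a defect.** Leaving a second instrument out of a model that already has the outcome's own baseline is ordinary practice, and the 09:40 PANAS-X is not wasted, since it can be the baseline for PANAS-X as an outcome. This is right as far as precision goes. It does not answer the timing problem, because the own baseline here comes after treatment.

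**PANAS-X is not a depression baseline.** It is a different instrument, given twice in one morning, which suggests a momentary measure; its correlation with a score taken after a 41-sachet phase may be low. The documents name no subscale, so negative affect is a choice made here. All this stands, and it is why the PANAS-X model belongs as a sensitivity analysis and a pre-drink BDI-II and PHQ-9 is the more direct remedy.

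**The sensitivity analysis is not a clean test.** A gap between the estimates mixes post-drink conditioning with chance imbalance and lost precision. This stands, and the working gives its size.

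**Two stronger readings are not supported.** A reader might infer that PANAS-X used in place of the 11:10 score improves precision, because against no mood covariate it removes 12% to 25% of the variance (0.35² to 0.50²). That is the wrong comparator: the plan already adjusts for baseline, and against that the swap never helps on these assumptions. A reader might also infer that the trial is short of power and needs the extra covariate. On one reading of the effect size it would be, but 60 is reproduced on another, and Section 1 gives too little to decide.

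**Conclusion.** The point holds as one about possible bias and an undefined baseline. The schedule settles that the only listed Visit 1 depression score follows the drink by an hour, and that the only listed pre-drink mood score is not used in the depression models. That the ANCOVA conditions on the 11:10 score rests on reading baseline values as each outcome's own.

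The direction and size of any bias are unknown. It is about 0.5 to 0.7 of whatever shift the drink causes at 11:10, and zero if there is none. The documents do not show that such a shift occurs.

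Lost precision is not established. Adding PANAS-X to the main model may gain nothing. This is a low-severity improvement, held with medium confidence; the figures depend on the assumed correlations.

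**What to change.** 1. **Define baseline values in Section 5**, naming the score and time for each outcome.

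2. **Prespecify a sensitivity ANCOVA** for Visit 2 BDI-II and PHQ-9, adjusted for 09:40 PANAS-X negative affect, sex and habitual fruit and vegetable intake, without the 11:10 score. State beside it that its residual variance is expected to be higher than with the own-baseline model (0% to 72% on the assumptions above, mid-case 25%), and that a gap between the estimates may reflect chance imbalance. Cost: a sentence or two and no new data. It also covers participants already tested, and should be fixed before unblinding.

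3. **Where recruitment is still open, collect BDI-II and PHQ-9 before the first drink**, for example at the existing screening session, and use that score as the baseline covariate. Cost: about 15 to 20 minutes per person, judging by the plan's own slots (11:10 to 11:25 at Visit 1, 09:30 to 09:50 at Visit 2). If some participants have already passed Visit 1, state which score enters the model for them.

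4. **Optional:** add 09:40 PANAS-X beside the 11:10 score in the main model, for 1 degree of freedom. This does not replace items 2 or 3.
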